Therefore, there is an opportunity to balance the advantages of both to optimize the performance of the binaural beamformer. This might be achieved through a change in the binaural beamformer strength. Today, in Paradise devices, the beamformer strength of SZ can be thought of as 70%. As such, the opportunity to change the beamformer strength could mean making the beamformer wider (<70%) or narrower (>70%), and both should be explored. In addition to the binaural beamformer strength, it would also be worthwhile to investigate the transition speed for binaural beamformer activation. The current transition speed for SZ is instantaneous (time constant = 0 sec.), which may be disturbing for some users. Elongating the transition time may result in a more pleasant user experience.

StereoZoom 2.0 is a new parameterization that balances the tradeoff between UZ and SZ. It has not yet been evaluated on human subjects. An evaluation of this feature with human subjects may identify which beamformer strength and transition speed settings strike the best balance between good directivity and spatial awareness while maintaining a pleasant user experience.

2 Objectives

The primary objective is to investigate the effect of binaural beamformer strength on spatial perception in speech in noise (SiN) environments through a subjective spatial awareness task comparing three beamformer strengths, including Stereozoom (SZ), with experienced hearing aid users with moderate hearing loss.

List of the secondary objectives:

- a. The secondary objective is to investigate the effect of binaural beamformer strength on speech intelligibility in noise through an objective SRT task comparing three beamformer strengths, including SZ, with experienced hearing aid users with moderate hearing loss.
- b. The secondary objective is to investigate the perceived benefit(s) of user steering of the binaural beamformer strength for SiN with experienced hearing aid users with moderate hearing loss.
- c. The secondary objective is to investigate the perceived benefit(s) of longer transition time (> 0 sec) for activation of the binaural beamformer through a comparison of multiple transition times with one beamformer strength, with experienced hearing aid users with moderate hearing loss.

3 Description of the investigational device

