This clinical investigation is intended to further development of the StereoZoom 2.0 feature. This feature will be available in future iterations of the Phonak Audeo hearing devices. The overall intended purpose of the device is to amplify and transmit sound to the ear and hereby compensate for impaired hearing.

4 Design of the clinical investigation

This interventional study will have 2-3 conditions per task for a sample population of 15-20 human subjects. The order of conditions will be counterbalanced and the participants will be blinded to the conditions.

5 Risks and benefits of the investigational device and clinical Investigation

There are minimal risks associated with both the investigational device and participating in the clinical investigation. The device used presents non-significant risk per FDA. The benefits of participating in the investigation include the benefit of personal satisfaction for participating in research to improve hearing instrument technology. Additionally, subjects will also be compensated for their time in participating in this study.

6 Endpoints

Primary endpoint: Subjective ratings of the beamformer strength conditions

- Subjective outcome parameters: 1) Perception of beamformer strength via a 100pt scale of 5pt increments from wide to narrow (0 = wide, 100 = narrow) and 2) Preference of beamformer strength via a 100pt scale of 5pt increments from not preferred to preferred (0 = not preferred, 100 = preferred).

Secondary endpoint: Objective and subjective measures

- Matrix Test outcome parameter: SRT 50%

- User steering of beamformer via a slider in a mobile app outcome parameter: subjectively perceived benefits measured via the grouping of the beamformer setting the user chose alongside their response to two questions:

1) Did you notice a change when moving the slider? (No difference, slight difference, clear difference)

2) Are you satisfied with what you could achieve with the slider? (Not satisfied, somewhat satisfied, definitely satisfied)

- Headphone recordings outcome parameter: Noticeability of beamformer transition in A/B comparisons comprised of 4 transition speeds.

7 Inclusion and Exclusion Criteria

Subjects fulfilling all of the following inclusion criteria are eligible for the investigation:

- 18-90 years of age
- Moderate to moderately severe (N3-N4) bilateral sensorineural hearing loss
- Fluent in English; ability to read and write in English
- Willing and able to provide informed consent

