- Participants must be experienced hearing aid users with symmetrical hearing loss defined as a difference of ≤ 10 dB between ears an air bone gaps ≤ 10 dB.
- Must be able to use app and smart phone.

The presence of any one of the following exclusion criteria will lead to the exclusion of the subject:

- Self-reported ear-related pathology (otorrhea w/in 90 days, dizziness, sudden hearing loss or worsening of hearing w/in 90 days, otalgia)
- Visible deformity of the ear
- Chronic, severe tinnitus
- Unilateral hearing loss
- Cognitive impairment
- Asymmetrical hearing loss
- Other diagnoses that may cause fluctuations in hearing (i.e. Meniere's)
- Unable to tolerate the physical fit of a RIC device
- Visual impairment that prevents the participant from seeing the adjustment slider in the mobile app
- Inability to be seen for 3 lab visits

8 Measurements and procedures

All home-trial data is locally stored on the participant's phone and will be manually extracted via a wired connection during their lab visits after each two week home trial. The extracted data is then saved in a company network drive.

All lab data is collected digitally. There are no paper questionnaires or result sheets in this investigation. The data files are saved in a company network drive after task completion.

All analysis of the results will occur at the conclusion of the study.

9 Statistical design and analysis

A priori sample size estimation was not performed for this investigation, as the investigation is exploratory and does not aim to confirm any effect with statistical significance and power.

This is an exploratory trial and will not have statistical criteria for termination.

Speech recognition thresholds will be recorded in dB SPL. SRT results will be recorded along with the anonymous participant ID, and task condition. Qualitative data will be collected as a question, response, and anonymous participant ID.

Analysis of the qualitative data will take place at the conclusion of the trial. Data (raw or trans-formed, per above) will be subjected to analysis via linear mixed effects modeling. The model will be constructed to regress (raw or transformed) subjective rating on a dummy variable of condition (fixed effect). This model will allow the investigators to evaluate the relative difference in subjective ratings between the beamformer strengths.

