Analysis of the SRT data and qualitative data related to the secondary objectives will take place at the conclusion of the trial, using similar methodology at described above.

10 Investigation Duration

Expected duration of each participant's participation is 4-5 weeks.

11 Data Handling and Management

Study data is recorded both with paper and with electronic Case Report Forms (p/eCRF). For each enrolled study participant a CRF is maintained. All CRFs are kept current to reflect the subject's status at each phase during the course of study. Participants cannot be identified in the CRF by name or initials and birth date but an appropriate coded identification is used. All study team members are authorized for the CRF entries and it is assured that any authorized person can be identified both for pCRFs and eCRFs. If pCRFs are used, the investigator's acronym as well as the subject ID is filled in and data are entered into an electronic file for analysis by the respective investigator and data get monitored by the assigned monitor. In case of a self-evident corrections, either the subject does it by himself or the investigator undertakes the correction by crossing out the word/sentence with a single horizontal line and by adding the correction including his personal identifier and the date.

Source documents for this investigation include, audiograms, Target fitting files, appointment checklists, data packages extracted from the app, and digital results packages exported from software used to collect data from lab tasks.

Any paper-based data will be stored in a locked filing cabinet at the investigation site. All electronic data will be stored on an access-restricted server owned, operated, and maintained by Sonova USA. Servers used to store data in this investigation are physically located in the US. Permission to access data will be limited to study manager, monitor, PI, and essential research staff, as designated by the principal investigator.

During data collection of the investigation, physical copies of the data will be compiled and digitized by the study manager on a daily basis. Data will be reviewed for misentries or inaccuracies as each data set is entered.

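### Does carrying one condition-dummy model over to the A/B and slider outcomes leave them without a usable analysis?

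*Combined protocol and SAP*

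**What the plan says.** Section 9 gives one model. It will "regress (raw or transformed) subjective rating on a dummy variable of condition (fixed effect", fitted as a linear mixed model, and its purpose is stated: "This model will allow the investigators to evaluate the relative difference in subjective ratings between the beamformer strengths". The secondary outcomes, SRT included, get a single sentence: "qualitative data related to the secondary objectives will take place at the conclusion of the trial, using similar methodology at described above".

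Section 6 defines two of those secondary outcomes. For the transition task it is "Noticeability of beamformer transition in A/B comparisons comprised of 4 transition speeds". For the slider it is "subjectively perceived benefits measured via the grouping of the beamformer setting the user chose alongside their response to two questions", and each question has three ordered answer categories.

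Section 4 sets the general layout: "This interventional study will have 2-3 conditions per task", counterbalanced and blinded, in 15-20 participants. Objective (c) in section 2 concerns "longer transition time (> 0 sec) for activation of the binaural beamformer through a comparison of multiple transition times", and section 1 supplies the comparator: "The current transition speed for SZ is instantaneous (time constant = 0 sec". No section states the A/B question, its answer options, which pairs are played, or the unit of analysis for either task.

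**The concern.** A condition dummy suits SRT, where each measurement is taken under one assigned beamformer strength. The other two secondary outcomes are built differently.

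- **A/B task.** The answer describes two recordings at once, so it is unclear what the dummy would code. If every pair contrasted a longer time with 0 s, differences between pairs would show how the longer times compare with one another. Objective (c) asks whether they improve on 0 s. All between-pair differences could be zero while every longer time was better than 0 s.
- **Count.** Two to three conditions per task and four speeds do not obviously agree.
- **Slider.** The setting is the participant's own choice, so a coefficient for it is not a randomised effect. Section 8 mentions more than one two-week home trial, so a participant may answer repeatedly and frequent users could dominate a pooled percentage.

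At stake would be the description of whether a slower transition is worth having, and of who is satisfied with the slider. No confirmatory test is involved.

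**Working it through.** The documents give no alpha, power, effect size or SD, so the only stated figure to check is the count. Inputs: four speeds (section 6); two to three conditions and 15-20 participants (section 4); 0 s as the current setting (section 1). Response rates below are assumed for illustration.

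1. **Count.** Speeds taken singly: 4. Unordered pairs: 4 × 3 / 2 = 6. Ordered pairs: 4 × 3 = 12. Pairs against one reference speed: 4 − 1 = 3. Only the last falls within two to three. It gives 15 × 3 = 45 to 20 × 3 = 60 answers at one answer per pair. The numbers can therefore agree, on a layout that the plan does not state.

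2. **Pair reading.** Assume forced choice, 0 s in every pair, and the dummy coded by pair. Let p1, p2, p3 be the shares favouring the longer time. The linear model gives b0 = p1, b2 = p2 − p1 and b3 = p3 − p1. Objective (c) wants each share minus 0.50, which is b0 − 0.50, b0 + b2 − 0.50 and b0 + b3 − 0.50.
   - All shares 80%: b2 = b3 = 0, and b0 − 0.50 = 0.30 for every pair.
   - Shares 60, 70 and 80%: b2 = 0.10 and b3 = 0.20. The departures are 0.60 − 0.50 = 0.10, 0.60 + 0.10 − 0.50 = 0.20 and 0.60 + 0.20 − 0.50 = 0.30.

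   The wanted quantity is recoverable from the fitted model in both cases. In the first case the contrasts vanish because the pairs were assumed equal. A condition test would then reject at about its nominal level, which says nothing about how likely that case is.

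3. **Single-recording reading.** The endpoint is noticeability of the transition, which can be scored for each recording. Assume 0 s is one of the four speeds and the reference level. Each coefficient is then the mean at a longer time minus the mean at 0 s. If 80% notice the transition at 0 s and 40% at each longer time, every coefficient is 0.40 − 0.80 = −0.40. That is objective (c) directly. The count is then 4, outside section 4's range, but the only consequence is three dummies in place of one or two.

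4. **What a prescribed alternative would bring.** Per-pair percentages with Wilson limits are one option: [p + z²/(2n) ± z√(p(1 − p)/n + z²/(4n²))] / (1 + z²/n), with z = 1.96. For 12/15 = 80% the limits are 55% and 93%; for 16/20 = 80% they are 58% and 92%. The widths are 38 and 34 points. This is a reasonable display, but it gives no single summary of the four speeds, and nothing in section 9 prevents it.

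5. **Slider.** Section 6 already tabulates answers by chosen setting, objective (b) asks about perceived benefit, and no section claims a causal effect of the setting. The plan proposes no pooled percentage, and a mixed-effects model ordinarily carries a participant term, which is the usual way to handle repeated answers.

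**The case for a change.** The strongest case for acting is that similar methodology describes no adaptation, so the scoring, the pairs and the unit could all be settled with the data in hand. Section 9 names only between-condition differences as the result, so the intercept might go unreported. Being exploratory removes the need for power, but a summary should still answer the stated objective.

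The warning about self-selection is also sound. Suppose a shared trait drives both the chosen setting and satisfaction, and the setting itself has no effect. Under assumed values, the top and bottom settings still differ by about 0.8 on a 0-2 score at 15-20 participants. Finally, section 9 lists only question, response and participant ID for qualitative data, without a pair or setting.

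It stands that the text is incomplete and that a slider coefficient must not be read as an effect. The rest weakens on inspection. Missing objective (c) requires forced choice, 0 s in every pair, coding by pair, equal preference in all three pairs and an ignored intercept, all together; the documents state none of these. The field list cannot be exhaustive: the primary ratings are analysed by condition, so condition must be stored with them, and section 6 needs the chosen setting beside each answer. Section 11 names app data packages and exported lab results as source documents. The wording would be cheap to alter in effort, but section 12 classes a change to the statistical plan as substantial, with a major version increment.

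**Conclusion.** No change is called for. Section 9 is brief about two secondary outcomes, but no analysis error is shown. Under the pair reading the model still contains each pair's departure from an even split; under the single-recording reading its coefficients answer objective (c) outright. The two-to-three against four discrepancy is an ambiguity that a three-pair layout resolves, and otherwise a loose description in section 4 with no effect on the result. The slider outcome is already defined by user choice and makes no causal claim.

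The undefined items (A/B question, answer options, pairs played, unit of analysis) are of the kind that analysts settle from the task as run. Candidate replacements, such as per-pair intervals or averaging within participant, are choices on which competent statisticians would differ. The size is nil for error rates, sample size and the primary analysis, and limited to clarity of description for the secondary ones.

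This rests on two assumptions: that the analysts read similar as adapted to each response format, and that the pair or setting is stored with each answer, as sections 6 and 11 imply.

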Informed consent will be obtained from participants prior to any study participation in accordance with the IRB guidelines. The participants will be granted sufficient time to read through the consent in full and ask any questions they have before signing. After the participant signs the consent form, the researcher will sign and provide a copy to the participant. This process will take place in a private office located in the Phonak Audiology Research Center (PARC). Participants will be incentivized with a monetary stipend of 30 USD per hour spent at the investigation site, plus mileage reimbursement for round-trip travel between the investigation site and their home address. Mileage reimbursement will be calculated based on the shortest driving distance in miles multiplied by the Internal Revenue Service's (IRS) standard mileage rate at the time the study concludes.

Informed Consent will only be obtained by investigation participants who can provide informed consent themselves before enrollment.

16 Adverse events, adverse device effects and device deficiencies

Device deficiencies and all **adverse events (AE)** including all **serious adverse events (SAE)** are collected, fully investigated and documented in the source document and appropriate case report form (CRF) during the entire investigation period, i.e. from participant's informed con-sent until the last protocol-specific procedure, including a safety follow-up period (ISO-14155, 2020). Documentation includes dates of event, treatment, resolution, assessment of serious-ness and causal relationship to device and/or investigation procedure.

Information on AEs is systematically collected during the regular investigation visits, and phone calls (if applicable).

The investigator(s) will follow-up on a biweekly basis with any participant experiencing an AE until either a) the participant reports resolution of the AE or b) 8 weeks have passed since the participant's final visit. If, however, the participant's condition worsens throughout the 8

week follow-up period, the investigator will continue to follow-up biweekly until the AE is resolved or the participant's condition stabilizes over an 8 week period.

The causality assessment of the SAE will be conducted according to MDCG 2020-10/1 Safety Reporting in Clinical Investigations of Medical Devices under Regulation (EU) 2017/745.

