The reporting of Serious Adverse Events and Device Deficiencies follows the Regulation (EU) 2017/745 and the MDCG 2020-10/1 Safety Reporting in Clinical Investigations of Medical Devices under Regulation (EU) 2017/745.

17 Vulnerable Populations

This investigation will not include any vulnerable populations.

18 Suspension or premature termination of the clinical investigation

The study will be terminated if the majority of the participants are not able to wear the devices for the study visit.

The study will be terminated if the participants or researchers are exposed to safety risks other than those outlined in this document.

The study may be terminated in the event natural disasters, widespread outbreak of illness, compromised structure of the investigation site, etc. that would make continuation of the study impossible or impractical. The study will be suspended within 5 days of determination that the study or device put participants at an unreasonable risk.

If a participant is suspended, terminated, or withdraws from the study, their data can be traced with their unique study identification number.

According to the FDA, follow-up is required for participants who experience Serious Adverse Events. Follow up will be conducted by the study manager and/or the PI until the nature of the event is resolved.

19 Publication policy

The clinical investigation will be registered in clinicaltrials.gov, a publicly accessible database, as required by U.S. regulations.

The results of the clinical investigation will be published on clinicaltrials.gov no later than one calendar year following the final participant appointment.

An internal report of the results of this investigation will be completed and uploaded to eQMS.

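### Do Sections 16 and 18 set conflicting end points for follow-up of serious adverse events?

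*Combined protocol and SAP*

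**What the plan says.** Section 16 (adverse events, adverse device effects and device deficiencies) opens with a broad scope: "Device deficiencies and all adverse events (AE) including all serious adverse events (SAE) are collected, fully investigated and documented". A separate paragraph then sets the follow-up duty: "The investigator(s) will follow-up on a biweekly basis with any participant experiencing an AE". That duty runs "until either a) the participant reports resolution of the AE or b) 8 weeks have passed since the participant's final visit". If the condition gets worse during those 8 weeks, "the investigator will continue to follow-up biweekly until the AE is resolved or the participant's condition stabilizes over an 8 week period". The only text in Section 16 specific to serious events concerns causality assessment and reporting, not the length of follow-up.

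Section 18 (suspension or premature termination) closes with two sentences on serious events: "According to the FDA, follow-up is required for participants who experience Serious Adverse Events", and then "Follow up will be conducted by the study manager and/or the PI until the nature of the event is resolved". No frequency, time limit or stability limit is given.

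Section 10 supplies the one other figure needed: "Expected duration of each participant's participation is 4-5 weeks".

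**The concern.** A serious adverse event is also an adverse event, and Section 16 names serious events in its opening sentence. A reader who consults only that section, which is where one would look, could conclude that an unresolved serious event may be closed 8 weeks after the final visit or, after worsening, once it has been stable for 8 weeks. Section 18 allows neither stopping point. It also sits under a heading where a reader with an adverse-event question might not look, and it gives the task to different roles. The document states no precedence.

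At stake is the completeness of the safety record: the final outcome of an unresolved serious event might never be captured, although Section 16 itself lists the date of resolution among the items to document. No efficacy endpoint or model is involved.

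**Working it through.** There is no sample-size, power or error-rate figure to reproduce. The check is a comparison of two stopping rules, plus one addition.

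**Inputs**

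| | Section 16 | Section 18 |
|---|---|---|
| Who is followed | any participant with an adverse event | participants with serious adverse events |
| By whom | investigator(s) | study manager and/or PI |
| How often | every two weeks | not stated |
| Ends at | reported resolution or 8 weeks after the final visit; after worsening, resolution or stability over 8 weeks | resolution, with no other limit stated |

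**Where the rules agree and differ**

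1. Non-serious event: only Section 16 applies, so there is no overlap.
2. Serious event that resolves within the 8 weeks: both duties end at resolution.
3. Serious event that has worsened and is neither resolved nor yet stable for 8 weeks: both duties continue.
4. Serious event, unresolved and not worsened at 8 weeks after the final visit: Section 16's duty has ended and Section 18's continues.
5. Serious event that worsened, then stayed stable but unresolved for 8 weeks: Section 16's duty has ended and Section 18's continues.

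The rules part only in cases 4 and 5, and always in the same direction. Section 16's end point never falls later than resolution (apart from the time a participant takes to report it), so Section 18's duty contains it. Section 16 says when biweekly contact is no longer required; it does not forbid further contact. No case exists in which obeying one section breaches the other.

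**Size of the difference**

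Taking the expected 4 to 5 weeks as the time from enrolment to final visit:

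- Case 4: 4 + 8 = 12 to 5 + 8 = 13 weeks after enrolment under Section 16.
- Case 5, assuming that the last worsening falls at the very end of the 8-week period and that stability is counted from then: 4 + 8 + 8 = 20 to 5 + 8 + 8 = 21 weeks. This illustrates one scenario and is not a ceiling, since further worsening would extend it.
- Section 18 states no upper limit in either case.

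**How the two sections fit together**

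The words that bring serious events into Section 16 belong to its sentence on collecting, investigating and documenting events. The follow-up paragraph is a default for adverse events of any kind. For serious events the protocol adds rules on causality, on reporting and, in Section 18, on follow-up. A general rule with a longer rule for the serious subset is an ordinary structure. The different roles and the unstated frequency in Section 18 fit this reading: the investigators' biweekly contact can end while the study manager or PI goes on following the event.

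**The case for a change.** The strongest case for a change is that none of this is written down. Section 16 expressly covers serious events, makes no exception for them in its follow-up paragraph, and gives no sign that another duration rule exists. The scope of Section 18 is also arguable. Its heading, and the preceding sentence about participants who are suspended, terminated or withdraw, could confine it to those settings, although its own wording is not so limited. Its end point is loosely phrased too: it refers to the nature of the event being resolved, and resolution of the event is only the natural reading. With the task split between roles, each could assume that the other has it. One sentence would remove the doubt.

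All of that stands as a remark on drafting. It does not show that a sentence is false or cannot be carried out. The harm requires staff to work from one section alone, whereas Section 13 holds the investigator to the plan as a whole and Section 18 names who is responsible. The protection from Section 13 is not complete, because it tolerates deviations that do not influence the investigation data. Even so, someone reading the whole document would find the duty in Section 18.

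**Conclusion.** No change to the plan follows. The difference in wording is genuine, but it is a missing cross-reference that staff applying the whole protocol can bridge, because following the longer-running duty satisfies both sections. It affects only a serious event still unresolved at Section 16's limit: about 12 to 13 weeks after enrolment without worsening, or about 20 to 21 weeks in the worsening scenario worked above. With 15 to 20 participants (Section 4) and risks described as minimal (Section 5), few such events are to be expected, if any, though the documents give no rate. No endpoint, estimate or conclusion of the trial would move.

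The conclusion assumes that Section 18 applies to every participant with a serious event, that its end point means resolution of the event, and that Section 16 sets a minimum and not a prohibition. If the sponsor revises the protocol for another reason, that would be a convenient time to reconcile the two sections and name the responsible role. Which follow-up rule is right is for the sponsor to settle, not this review.
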